8.3 Compliance with clinical investigation intervention

As the examinations will be performed only once in this study there are no concerns with patient compliance.

8.4 Data Collection and Follow-up for withdrawn subjects

As this is a clinical study where most participants are imaged only once, there are no concerns with data collection from withdrawn subjects. Data from withdrawn subjects will be anonymized and evaluated as far possible according to Art. 3 Abs. b ClinO-MD. If a subject withdraws from the investigation, the reason of withdrawal will be asked and recorded. If such withdrawal is related to the SPECTRALIS HighRes-OCT ®, the PI will ask for the subject's permission to follow his/her condition outside the investigation, using routine (standard) examinations. The medical follow-up of withdrawn subjects, or of subjects that drop out from the investigation prematurely is described in chapter 9.2.5 and chapter 9.2.6.

8.5 Clinical investigation specific preventive measures

Not applicable.

8.6 Concomitant Interventions (treatments)

Not applicable.

8.7 Medical Device Accountability

The SPECTRALIS HighRes-OCT ® has been provisioned by Heidelberg Engineering GmbH, 69115 Heidelberg/Germany to the department of Ophthalmology at the university hospital Bern, Inselspita. Maintenance and support is provided by Heidelberg Engineering GmbH - 8105 Regensdorf – Switzerland.

8.8 Return, Analysis or Destruction of the Medical Device

Return of this device is according to standard procedures of the Inselspital Bern.

9. CLINICAL INVESTIGATION ASSESSMENTS

9.1 Clinical investigation flow chart(s) / table of clinical investigation procedures and assessments

There will be a consecutive ongoing recruitment of patients and healthy subjects attending routine follow-ups through the involved investigators in daily clinical practice at Department of Ophthalmology, Inselspital, Bern. Recruitment will last from October 2021 to November 2023. Patients, who fulfilled the indication of either SD-OCT or fluorescein angiography imaging for diagnosis of retinal/optic nerve disease will be included and additional imaging will be performed with the High-Res-OCT.

Subject	Initial imaging with High-Res-OCT
Healthy volunteers	X ₁
Patients with retinal/optic nerve disease	X ₁
X =mandatory imaging session. ¹ routine imaging with either SD-OCT, fundus photography or fluorescein angiography according to clinical routine	

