3.6 Explanation for choice of comparator

The comparator in this study is conventional imaging of the retina with fluorescein angiography and standard SD-OCT. The fluorescein angiography allows to image the retinal vasculature using a dye and is routinely performed in clinical routine for diagnosis of retinal vasculopathies. Fluorescein angiography (FA) and indocyanine green angiography (ICGA) are both invasive test that require intravenous administration of dye and imaging up to 10–30 minutes²⁶. The SD-OCT is used in the clinical routine and allows to image the retinal structure with an axial resolution of approximately 7 μm .

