4. CLINICAL INVESTIGATION OBJECTIVES

4.1 Overall Objective

The study aim is to investigate the diagnostic accuracy of the High-Resolution OCT in comparison with conventional imaging methods and whether High-Resolution OCT can reliably diagnose retinopathies thereby making more invasive investigations such as fluorescein angiography or conventional imaging methods futile. The main goal is to facilitate diagnosis of eye diseases for individual patients.

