11. STATISTICAL METHODS

11.1 Hypothesis

The primary variable in this study is the ability to detect pathological changes in the retina/optic nerve in comparison to conventional imaging modalities such as SD-OCT, color fundus photography and fluorescein angiography.

Null hypothesis: there is no difference in detecting pathological changes in the retina/optic nerve between conventional imaging and High-Resolution OCT

Alternative hypothesis: there is a difference in detecting pathological changes in the retina/optic nerve between conventional imaging and High-Resolution OCT

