11.2 Determination of Sample Size

The primary variable for this assessment is the ability to detect the presence of retinal structural abnormalities with High-Res-OCT in comparison to conventional ophthalmic imaging methods, mainly SD-OCT. This will result in a binary outcome. Assuming that the accuracy of each of these conventional imaging modalities separately is 90%, and there is truly no difference between the conventional imaging and High-Res-OCT (null hypothesis), then 550 patients are required to be 90% certain that the upper limit of a one-sided 95% confidence interval (or equivalently a 90% two-sided confidence interval) will exclude a difference in favor of the conventional imaging of more than 10%¹⁶.

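### The primary comparator is not fixed for each participant, so a single contrast with conventional imaging depends on the modality mix and can mask inferiority to SD-OCT

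*Combined protocol and SAP*

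**What the plan says.** In section 9.1 the only mandatory imaging is High-Res-OCT. The footnote to the procedures table gives the comparator as "routine imaging with either SD-OCT, fundus photography or fluorescein angiography according to clinical routine". The entry sentence in the same section names two modalities rather than three: "Patients, who fulfilled the indication of either SD-OCT or fluorescein angiography imaging for diagnosis of retinal/optic nerve disease will be included".

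The comparator is described differently elsewhere:

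- Section 3.6: "The comparator in this study is conventional imaging of the retina with fluorescein angiography and standard SD-OCT".
- Section 11.2 (and the synopsis): "in comparison to conventional ophthalmic imaging methods, mainly SD-OCT".
- Sections 5.1, 11.1 and 11.4: SD-OCT (or OCT), colour fundus photography and fluorescein angiography together.

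The null hypothesis in 11.1 has a single comparator: "there is no difference in detecting pathological changes in the retina/optic nerve between conventional imaging and High-Resolution OCT". Section 11.4 plans one one-sided 95% interval for it. The sample-size text begins "Assuming that the accuracy of each of these conventional imaging modalities separately is 90" per cent, but no modality-by-modality test follows in 11.4 to 11.4.3, where the subgroups are by disease only. The nearest secondary outcome (5.2) is again an either/or set, SD-OCT or fundus photography. It is a correlation with no margin. The examination form (12.1.2) records SD-OCT and angiography only where applicable.

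Section 4.1 also asks whether High-Res-OCT can diagnose reliably enough for "making more invasive investigations such as fluorescein angiography or conventional imaging methods futile".

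**The concern.** A non-inferiority margin has meaning only against a stated comparator. Here the comparator can differ between participants according to why they were imaged. One combined difference is then a weighted average of up to three contrasts, and the weights come from referral patterns rather than from the design. A deficit against SD-OCT, the modality that the sample-size text calls the main one, can be diluted by participants who were compared with something else.

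The mix probably follows diagnosis. Section 3.6 says that angiography "is routinely performed in clinical routine for diagnosis of retinal vasculopathies", and modality choice is left to clinical routine. If so, two centres with different case mix could reach different conclusions about the same device.

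The aim about angiography is exposed as well. Only participants who had angiography for clinical reasons can inform it, and they have no planned analysis, number or margin of their own.

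**Working it through.** **The plan's own figure.** Inputs from 11.2: accuracy 90% on both sides, margin 10 points, one-sided 5%, power 90%, N = 550. With independent errors within a pair, the variance per pair is 0.9×0.1 + 0.9×0.1 = 0.18, so

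n = (1.645 + 1.282)² × 0.18 / 0.10² = 154.2, i.e. 155 pairs (or 155 per group, 310 in all, if unpaired).

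Section 11.4.2 gives a second basis: error 0.03, sensitivity 0.90, prevalence 0.9. At 95% confidence this is 1.96² × 0.09 / 0.03² / 0.9 = 427. Neither gives 550. That is a separate matter and does not affect this point; 550 is used below as the planned number.

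**How often a combined test passes.** Let w be the share of participants whose comparator is SD-OCT. Assumptions, not in the documents: w itself; independent errors within pairs; in SD-OCT participants, SD-OCT 90% and High-Res-OCT 80% accurate; in all others, comparator and High-Res-OCT both 90%. Every comparator thus keeps the 90% that 11.2 assigns to it.

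- Combined difference: d = w × (−0.10) + (1 − w) × 0.
- Variance per pair: V = w × (0.16 + 0.09) + (1 − w) × (0.09 + 0.09) + w(1 − w) × 0.10².
- Pass probability: Φ[(0.10 + d)/√(V/550) − 1.645].

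| w | d | V | SE | z | Passes |
|---|---|---|---|---|---|
| 0.5 | −0.05 | 0.2175 | 0.0199 | 0.87 | 81% |
| 0.7 | −0.07 | 0.2311 | 0.0205 | −0.18 | 43% |
| 0.8 | −0.08 | 0.2376 | 0.0208 | −0.68 | 25% |
| 0.9 | −0.09 | 0.2439 | 0.0211 | −1.17 | 12% |
| 1.0 | −0.10 | 0.2500 | 0.0213 | −1.645 | 5% |

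A test restricted to SD-OCT pairs passes 5% of the time in each row, because the true deficit sits on the margin.

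If High-Res-OCT is instead 10 points better than the other modalities (90% against 80%), the pass rates are 99.8%, 87%, 58% and 24% at w = 0.5, 0.7, 0.8 and 0.9.

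**What an SD-OCT-only primary set can deliver.**

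- Overall accuracy: 155 pairs, which is 155/550 = 28% of all participants.
- Specificity: if the 100 healthy subjects supply the negatives (assumption), power is Φ[0.10/√(0.18/100) − 1.645] = Φ(0.71) = 76%. With 80 or 60 of them it is 68% or 57%.
- Sensitivity precision at prevalence 0.9: half-width 1.96 × √(0.09/(0.9n)), which is ±0.026 at n = 550, ±0.034 at n = 330 (60% of 550), and ±0.050 at n = 155. The target in 11.4.2 is ±0.03.

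**The case against.** The strongest reply is that the plan already leans towards SD-OCT. Section 11.2 says so, 3.6 omits fundus photography, and the entry sentence in 9.1 does not list fundus photography as an indication. If 90% or more of participants have SD-OCT, the inflation in the table is 12% against 5%. This stands as a limit on size. It does not remove the ambiguity, because no section guarantees SD-OCT or states its share, and the footnote in 9.1 says otherwise.

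The plan also never says that the modalities will be pooled, and 11.2 assumes an accuracy for each one separately. That is fair: the combined contrast is a reading drawn from the single hypothesis, the single interval and the absence of any split. Dependence on diagnosis is likewise an inference, as no table gives modality by disease. Participants may also have several modalities. A comparison with routine imaging as actually used is an interpretable pragmatic contrast, so it would go too far to call the combined result meaningless.

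Two stronger inferences are not supported. A reader might infer that restricting the primary analysis to SD-OCT pairs is free because only 155 are needed. That number covers overall accuracy alone. The primary outcome is sensitivity and specificity, and no SD-OCT share is given. A reader might also infer that High-Res-OCT will pass because it outperforms fundus photography. The documents contain no evidence that it does, and the main calculation here does not assume it.

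**Conclusion.** The point holds. The primary comparator is not defined at participant level, the sections disagree on what it is, and one margin is applied to it. Read as one combined contrast, the test can pass for a device that is at the margin against SD-OCT in about 81%, 43%, 25% or 12% of trials at SD-OCT shares of 50%, 70%, 80% or 90%, against a nominal 5%. These rates rest on N = 550, independent errors, an assumed SD-OCT share and equality with the other modalities. They show what the wording permits, not what will happen, and the effect is modest if nearly all participants have SD-OCT. The aim concerning angiography has no dedicated analysis behind it.

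**What to change.** - In 9.1, 11.1, 11.2, 11.4 and 11.4.2, name SD-OCT of the same eye at the same visit as the sole primary comparator, analysed as pairs. Bring 3.6, 5.1 and the synopsis into line. This also settles which modality counts in the primary analysis when a participant has several.
- Analyse fundus photography and fluorescein angiography as separate secondary contrasts, each in the participants who had that modality and with its own number.
- Report modality by diagnosis.
- In 3.1 and 4.1, limit the claim that other investigations become unnecessary to what the angiography subset shows.
- State the expected number of SD-OCT pairs, among patients and among healthy subjects, with the resulting power and precision.

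The cost is mainly wording, plus a smaller primary set: participants without SD-OCT, including those with angiography only, move to the secondary contrasts even though 3.6 names angiography as a comparator. Overall accuracy keeps 90% power down to 155 pairs under the plan's inputs with independent errors. Specificity (about 76% power with 100 negatives) and the ±0.03 sensitivity target (about ±0.034 with 330 participants) may fall short, which is why the expected number of pairs has to be given.

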9.2 Assessments of outcomes

[figure not shown]

Fig. 2: Switching the device on and off

- ① Isolating transformer
- ② Power supply
- ③ PC
- ④ Monitor

The high-quality images of the retinal structures acquired with the SPECTRALIS HighRes-OCT ® will be obtained as follow:

- Power on the unit and log on
- Enter, find, and modify patient identifying data
- Clean surfaces that contact patient
- Position patient with the device, including moving the patient, the device, the table height, and the patient's chair
- Select and acquire scan
- Review and save scan or try again
- Generate reports using available reporting protocols
- Review reports for completeness
- Output reports
- Archive data
- Turn off the unit

The operators will be trained Heidelberg Engineering GmbH - 8105 Regensdorf – Switzerland, which will also calibrate the medical device and offers maintenance and support.

The data analysis will be performed by the investigator with the appropriate professional training or experience in the use of ophthalmic imaging equipment.

9.2.1 Assessment of primary outcome

The sensitivity and specificity of the High-Resolution OCT to diagnose the presence/absence of pathological changes in the retina/optic nerve in comparison to conventional imaging modalities will be assessed as a primary outcome. The following pathological changes will be assessed: intraretinal or subretinal fluid, pigment epithelial detachment, epiretinal membrane, substance defect, drusen, hyperreflective foci, atrophy, neovascularization, choroid abnormalities, scars, optic nerve swelling and ischemia. For each of these pathological changes a binary outcome will result. Additionally, study participants will be asked to consent to prospective collection of clinical and demographic data, to correlate findings of High-Res-OCT imaging to subsequent clinical course.

There is no need to be in a particular posture before the examination in order to obtain high quality images. The participants will be in a sitting position during the examination during approximately 30-60 seconds per eye. In case the measurement needs to be repeated, no waiting period will be necessary. A repeated measurement needs to be recorded in the CRF.

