4.2 Primary Objective

The primary objective of this study is to evaluate the sensitivity and specificity to diagnose retinal morphological abnormalities with High-Resolution OCT compared to conventional imaging methods, such as SD-OCT, fluorescein angiography. The main parameters, which will be assessed are the presence of morphological abnormalities (such as but not limited to intraretinal or subretinal fluid, epiretinal membrane, substance defect, drusen, hyperreflective foci, atrophy, neovascularization, optic nerve, swelling, choroid abnormalities, scars, ischemia) within the macula and optic nerve head. The incidence (binary) and diagnostic accuracy of these morphological abnormalities will be assessed in High-Res-OCT and compared to conventional imaging methods such as SD-OCT.

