5. CLINICAL INVESTIGATION OUTCOMES

5.1 Primary Outcome

The primary outcome as measured on the individual patient-level is whether High-Resolution OCT has a similar or higher specificity and sensitivity to detect pathological changes in the retina/optic nerve as conventional imaging methods, such as SD-OCT, color fundus photography and fluorescein angiography. This will result in a binary outcome. Pathological morphological changes includes but are not limited to, intraretinal or subretinal fluid, epiretinal membrane, substance defect, drusen, hyperreflective foci, atrophy, neovascularization, optic nerve swelling, choroid abnormalities, scars, ischemia. Additionally, study participants will be asked to consent to prospective collection of clinical and demographic data, to correlate findings of High-Resolution OCT imaging to subsequent clinical course.

Ophthalmic diseases include, but are not limited to:

- Retinal vascular diseases
- Retinal detachment
- Hereditary retinal diseases/dystrophies
- Glaucoma
- Optic nerve neuropathy
- Inflammatory/infectious retinal diseases

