11.4.2 Primary Analysis

The results will be displayed using a receiver operating characteristic (ROC), or ROC curve. The curve is created by plotting the true positive rate (TPR) against the false positive rate (FPR) at various threshold settings. Here the required total sample size for estimating sensitivity (presence of the pathological changes within the scans) with respect to marginal error (0.03), sensitivity (90%) and the prevalence (0.9) of disease in target population would be approximately 550 subjects¹⁷. Depending on the results, precision and recall (PR) curves are also going to be computed, which are useful in case of distribution imbalance between two classes of a binary model, specifically if the true negative values are high, the latter not being taken into account in the calculation³⁰. Precision (Y-axis) is referred as the positive predictive value and recall (X-axis) as sensitivity. A high precision value means that the tested classifier/device provides accurate results, while high recall indicates that the majority of all positive samples were detected. The possible AUC value ranges from 0.5 (discriminative performance equal to chance) to 1.00 (perfect discriminative performance). The primary analysis will be done using

Python 3 and its open-source package Scikit-learn v0.20.3.

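### The primary outcome is one patient-level binary in 5.1 and section 11 but twelve lesion-level binaries in 9.2.1, with no rule for combining them, choosing the comparator or handling multiplicity

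*Combined protocol and SAP*

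**What the plan says.** Section 5.1 sets the level of the outcome, "The primary outcome as measured on the individual patient-level", and its form, "This will result in a binary outcome". Section 11 follows this. Section 11.2 justifies 550 subjects with one accuracy (90%), one margin (10 points) and one one-sided 95% interval. Section 11.4 tests with one such interval. Section 11.4.2 gives one sensitivity (90%), one margin of error (0.03) and one prevalence, "the prevalence (0.9) of disease in target population".

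Section 9.2.1 opens with sensitivity and specificity for the presence or absence of pathological changes. It then names twelve changes and states: "For each of these pathological changes a binary outcome will result".

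The lists also differ. Section 5.1 is open ("Pathological morphological changes includes but are not limited to"), as are section 4.2 ("such as but not limited to intraretinal or subretinal fluid, epiretinal membrane, substance defect, drusen, hyperreflective foci, atrophy, neovascularization") and the synopsis. The list in 9.2.1 is closed. Among these primary-outcome lists, pigment epithelial detachment appears only in 9.2.1, and optic nerve swelling is missing from the synopsis.

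Sections 5.1, 11.1 and 11.4 name SD-OCT, colour fundus photography and fluorescein angiography as comparators. Section 11.2 says that SD-OCT is the main one. The study is open label (6.2), and blinding and other bias controls are marked not applicable (6.2.2, 6.2.3). Section 11.4.5 lets the analysis be adapted when interesting questions arise during analysis, provided that deviations are described and justified.

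**The concern.** A reader cannot tell from the plan which result decides the study. It could be a single patient-level call, any one of twelve lesions, all twelve, or a lesion added under the open wording of 5.1. It could also be any of these against any of three comparators. The readers are not masked and the analysis may be adapted, so the choice could be made once results are known. The rules also have very different operating characteristics. The 5% error rate, the 90% power and the ±3-point precision are all argued for one variable, and do not carry over automatically to a lesion-level reading.

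**Working it through.** **Inputs from the documents.** N = 550, of whom 450 have diagnosed disease in nine groups of 50 and 100 are healthy (6.1). One-sided 5%, 90% power, 10-point margin, accuracy 90% (11.2). Sensitivity 0.90, margin of error 0.03, prevalence 0.9 (11.4.2). Twelve lesions, with intraretinal or subretinal fluid counted as one item (9.2.1).

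**Not in the documents, so assumed.** A 95% two-sided level for the margin of error; lesion prevalence; correlation between lesions; per-lesion specificity.

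1. *The plan's own precision figure.* Positives needed = 1.96² × 0.90 × 0.10 / 0.03² = 384.1, so 385. Dividing 384.1 by 0.9 gives 427 subjects, not 550. At the planned mix of 450/550 = 0.818 it gives 470. That 550 does not follow from its inputs is a separate matter. Here it means that 550 is more than enough at patient level.

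2. *Precision at patient level.* Half-width = 1.96 × √(0.09/n). With n = 0.9 × 550 = 495 it is ±2.6 points. With n = 450 it is ±2.8 points. The ±3 holds.

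3. *Precision at lesion level.* ±3 points needs 385 patients with that lesion, and 385/550 = 70%. For all twelve lesions to reach it, 12 × 385 = 4,620 lesion-positive findings are needed. If these come from the diseased patients, that is 4,620/450 = 10.3 of the twelve lesions per patient, across nine different diseases. For an assumed range of prevalence:

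| Assumed lesion prevalence | Positives in 550 | Half-width |
|---|---|---|
| 5% | 27.5 | ±11.2 points |
| 10% | 55 | ±7.9 points |
| 20% | 110 | ±5.6 points |

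4. *Error rate and power under each possible rule.* Under the interval rule of 11.4, a lesion is at the null when High-Res-OCT is truly worse by exactly the margin.
   - Any lesion counts, or lesions are claimed separately: with all twelve at the null, 1 − 0.95¹² = 46.0% if independent. It is 5% if fully correlated, and the Bonferroni bound is 12 × 5% = 60%.
   - All twelve must succeed: type I error stays at or below 5%. With 90% power assumed for each, joint power is 0.90¹² = 28.2% if independent.
   - One patient-level binary decides: type I error is 5%.

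5. *Power for a single lesion.* Carrying the 10-point margin over to one lesion, with independent readings and no adjustment, power = Φ(0.10/√(0.18/n) − 1.645). This is 76% with n = 100 positives and 51% with n = 50.

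6. *Comparators.* Three comparators, any one sufficing, give 1 − 0.95³ = 14.3% if independent. Sharing the same High-Res-OCT reading would normally lower this.

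7. *What an any-lesion call does to specificity (illustration).* If each lesion had 97% specificity and false positives were independent, patient-level specificity would be 0.97¹² = 69%. Reaching 90% would need 0.90^(1/12) = 99.1% per lesion.

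**The case against.** The best defence is that 9.2.1 begins with a single primary outcome and that its later sentence only describes how images are scored, with the scores feeding the patient-level binary of 5.1. Section 11 fits this reading: it has one variable and one interval, and nowhere plans twelve primary tests or claims ±3 points per lesion. The defence is reasonable and narrows the point. It does not remove it, because no section states the step from lesion scores to the patient-level call.

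Three stronger readings are tempting, and the documents do not support them.
- A reader might infer that the study runs twelve primary tests and so has a 46% error rate. That figure needs any-lesion success, independence and every lesion at the null; the plan states none of these.
- A reader might infer that the ±3-point precision is wrong for the primary outcome. At patient level it is met.
- A reader might infer that the assessment list itself is open-ended. The list in 9.2.1 is closed; the open wording is in the synopsis, 4.2 and 5.1.

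The choice of outcome after the fact is likewise a possibility that the plan leaves open, not something it proposes. The requirement in 11.4.5 to describe and justify deviations gives disclosure, but it does not fix the deciding outcome in advance.

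It can also be objected that an any-lesion call is a weak primary outcome: it credits the wrong lesion and accumulates false positives. That stands, and the fix has to deal with it.

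**Conclusion.** The point holds as an unresolved inconsistency. Sections 5.1 and 11 imply one patient-level variable, while 9.2.1 produces twelve lesion-level binaries as the primary assessment. The combining rule, the deciding comparator and the multiplicity rule are all missing, and the lesion lists disagree. The size depends on the rule that is eventually chosen: anywhere from no inflation (5%) to 46% under independence for any-lesion success, or about 28% joint power if all twelve must succeed. The ±3 points is sound at patient level and fails for any lesion present in fewer than about 385 of 550 patients. The lesion half-widths and the 69% specificity are illustrations over assumed values, since neither lesion prevalence nor per-lesion specificity is in the documents. The patient-level outcome is workable once it is named as the only primary one.

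**What to change.** - **Primary outcome.** In 5.1, 9.2.1, 11.4 and 11.4.2, state one primary outcome: the patient-level call that any listed pathological change is present, against one primary comparator, SD-OCT, which 11.2 already calls the main one.
- **List.** In the synopsis, 4.2 and 5.1, close the primary-outcome list to the one in 9.2.1. The separate subgroup list in 9.2.2 can stay.
- **Secondary comparisons.** Make the twelve lesion-level paired comparisons and the other two comparators secondary, with Holm adjustment across the lesions.
- **Lesion-matched analysis.** Pre-specify a secondary analysis in which a patient is a true positive only if a lesion present on the reference is the one called. Report it beside the primary, because the any-lesion call credits wrong-lesion detections and accumulates false positives.
- **Precision.** State that ±3 points applies only to the patient-level outcome.

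This is wording in the protocol and analysis sections, with no added subjects. The main cost is that lesion-specific claims face a stricter threshold. One consequence needs a sentence: 9.1 has routine imaging with SD-OCT, fundus photography or fluorescein angiography as clinically indicated, so the plan should say how subjects without an SD-OCT are handled in the primary comparison. Their number cannot be judged from the documents.
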